7.3. Clinical Laboratory Test and Normal Laboratory Ranges

Each standard clinical laboratory test, i.e., CBC, serum comprehensive metabolic panel and urinalysis, will be performed by a single laboratory for all subjects enrolled in the study. The laboratory that will perform these tests required by the protocol must transmit normal ranges of the clinical laboratory tests to Amphastar Pharmaceuticals, Inc. Urinary pregnancy and 9 panel drug tests may be performed using a clinically accepted test kit.

8. STUDY MONITORING, DOCUMENTATION AND RECORD KEEPING

8.1. Data Quality Assurance and Monitoring

The trial will be monitored according to the current Amphastar SOP.

The site monitor will conduct monitoring of the investigational activities for the purpose of ensuring subject safety and study compliance to applicable regulatory guidelines. The Investigator will permit Amphastar authorized monitors to access the subject source documents, eCRFs, clinical supplies dispensing and storage area and study documentation as frequently as necessary and agrees to assist the site monitors with their activities. The study site will make the eCRF available, provide missing or correct data and PI will sign the eCRFs. Personal or subject identifying information will be treated as confidential and will NOT be publicly accessible.

The trial information may be reviewed by regulatory authorities or independent QA auditors. The study site may be inspected during or after completing the study. The Investigators agree to allow inspectors from regulatory agencies to have access to all trial records, including subject source documents. By participating in this study, the Investigator

8.2. Electronic Case Report Forms (eCRFs)

Electronic Data Capture (EDC) system will be used for recording of electronic CRF (eCRF) for the conduct of the study by Amphastar, eCRF will be used for the purpose of capturing data for all consented participants in the study. The 24 hour clock will be used for all time entries.

Subject source documents are the study subject records maintained at the study site. In some cases, the source documents may be the hospital's or the physician's clinical records. Therefore, the information collected on the eCRFs must match those records. Amphastar personnel will review all eCRFs to ensure the data is verifiable and accurate. At all times, the PI has final responsibility for the accuracy and authenticity of all clinical and laboratory data entered on the eCRFs. The eCRFs will be completed as soon as possible after the data become available.

8.3. Clinical Trial Drug Accountability Data

The Study Site Research Pharmacist or designated dispenser acknowledges that the drug supplies are investigational and, as such, must be handled in accordance with the protocol and labeling. The Research Pharmacist or designated personnel will maintain adequate

records showing the receipt, dispensing, return, or other disposition of the investigational study material, including the date, quantity, lot or code number, and identification of subjects (number, initials) who received or returned study drug.

The Research Pharmacist or designated dispenser and Amphastar's unblinded site monitor will review study supply records, including dispensing and accountability records, at monitoring visits.

It is the responsibility of the Investigator and research pharmacist/designated dispenser to ensure that, when the study is completed or discontinued, unused study supplies will be returned or disposed of, as directed by Amphastar's site monitors or CRA. Unused and returned medication must be available for verification by Amphastar's site monitors or CRA.

8.4. Trial Documents

The trial documents, including the protocol signature page signed by the Investigators, Investigators' curriculum vitae, IRB approval notice and IRB member list, approved Informed Consent Form, laboratory verification and institutional accreditation, will be submitted to Amphastar Pharmaceuticals, Inc.

8.5. Reporting and Publication

The clinical trial report will be prepared according to the Amphastar SOP for Clinical Trial Reporting.

8.6. Archive

The Investigator will retain a copy of all study documents, including reports to the IRB/Ethics Committee and to the sponsor, in accordance with the FDA and local regulations. The FDA regulations and/or ICH guidelines state that the Investigator must maintain study documents for a set period of time. The Investigator will arrange for the retention of the Subject Identification for at least 15 years after the Final Study Report has been signed. All other documents should be kept for the maximum period of time permitted by the institution.

9. ETHICS

9.1. Institutional Review Board (IRB) or Ethics Committee Approval

This study will be conducted in conformance with all regulatory guidelines, particularly the FDA guidance on MDI and DPI drug products^[1]. This trial can be conducted only after full approval of the final protocol (and its addendum) has been obtained from the involved Institutional Review Board (IRB) or Ethics Committee. The approval must be received by Amphastar before the initiation of the study.

9.2. ICH GCP Guidelines and Declaration of Helsinki

This trial will be undertaken in accordance with the current ICH Good Clinical Practice (GCP) guidelines and adheres to the core principles of the Declaration of Helsinki of the World Medical Association to assure that the rights, safety and well-being of the study subjects are protected.

9.3. Informed Consent

The Investigator must explain to subjects the purpose, methods, potential benefits and risks of the trial. Subjects will be informed that they are free not to participate in the trial and they may withdraw from the study at any time. Written informed consent from each subject enrolled in the study, in accordance with the Code of Federal Regulations Title 21, Part 50, Subpart B will be recorded by means of dated signatures of the subjects.

Informed Consent will include authorization to use data from the trial for all purposes relating to approval of the drug under investigation.

9.4. HIPAA Compliance

The Investigator is responsible for compliance with the privacy provisions of the Health Insurance Portability and Accountability Act including obtaining informed consent for use of data for marketing purposes.

Appendix II. Body Mass Index (BMI) Table

BMI Formula:

$$\text{BMI} = \text{Weight [in kilograms]} / (\text{Height [in meters]})^2 \quad \text{Or}$$

$$\text{BMI} = \text{Weight [in pounds]} \times 703.7 / (\text{height [in inches]})^2$$

HEIGHT		BMI CHART																											
feet/ inches	cm	12	13	13	14	15	16	17	18	18	19	20	21	22	22	23	24	24	26	26	27	28	29	29	30	31	32	33	34
6'4"	192.5	12	13	13	14	15	16	17	18	18	19	20	21	22	22	23	24	24	26	26	27	28	29	29	30	31	32	33	34
6'3"	190	12	13	14	15	16	16	17	18	18	19	20	21	22	23	24	24	25	26	27	28	29	29	30	31	32	33	34	34
6'2"	187.5	13	13	14	15	16	17	18	18	19	20	21	22	23	24	24	25	26	27	28	29	29	30	31	32	33	34	34	36
6'1"	185	13	14	15	15	16	17	18	19	20	21	22	22	23	24	24	25	26	27	28	29	29	30	31	32	33	34	34	36
6'0"	182.5	13	14	15	16	17	18	19	20	20	21	22	22	23	24	24	25	26	27	28	29	29	30	31	32	33	34	34	37
5'11"	180	14	15	15	16	17	18	19	20	21	22	23	24	24	24	25	26	27	27	28	29	29	30	31	32	33	34	34	36
5'10"	177.5	14	15	16	17	18	19	20	21	22	23	23	24	25	26	27	28	29	30	31	32	33	34	34	36	37	38	39	40
5'9"	175	14	15	16	17	18	19	20	21	22	23	24	25	26	27	28	29	30	31	32	33	34	34	36	37	38	39	40	41
5'8"	172.5	15	16	17	18	19	20	21	22	23	24	24	26	27	28	29	29	31	32	33	34	34	36	37	38	39	40	41	42
5'7"	170	15	16	17	18	19	20	21	22	24	24	26	27	28	29	29	31	32	33	34	34	36	37	38	39	40	41	42	43
5'6"	167.5	16	17	18	19	20	21	22	23	24	25	26	27	29	29	31	32	33	34	34	36	37	38	39	40	41	42	43	45
5'5"	165	16	17	18	19	20	21	22	23	24	24	26	27	28	29	30	31	32	33	34	34	36	37	38	39	40	41	42	46
5'4"	162.5	17	18	19	20	21	22	23	24	26	27	28	29	30	31	33	34	34	36	37	38	39	41	42	43	44	45	46	47
5'3"	160	17	18	20	21	22	23	24	25	27	28	29	30	31	32	34	34	36	37	38	39	41	42	43	44	45	46	48	49
5'2"	157.5	18	19	20	21	23	24	24	26	27	29	29	31	32	33	34	36	37	38	40	41	42	43	44	46	47	48	49	50
5'1"	155	18	20	21	22	23	24	26	27	28	29	31	32	33	34	36	37	38	40	41	42	43	45	46	47	48	50	51	52
5'0"	152.5	19	20	21	23	24	25	27	28	29	31	32	33	34	36	37	38	40	41	42	43	45	46	47	49	50	51	52	54
4'11"	150	20	21	22	24	24	26	28	29	30	32	33	34	36	37	38	40	41	42	44	45	46	48	49	50	52	53	54	56
4'10"	147.5	20	22	23	24	26	27	28	29	31	33	34	35	37	38	40	41	42	44	45	46	48	49	51	52	53	55	56	57
4'9"	145	21	22	24	25	27	28	29	31	32	34	35	37	38	39	41	42	44	45	47	48	49	51	52	54	55	57	58	59
4'8"	142.5	22	23	24	26	28	29	31	32	33	34	36	38	39	41	42	44	45	47	48	50	51	53	54	56	57	59	60	62
WEIGHT (kg)		44	47	50	53	56	59	62	65	68	71	74	77	80	83	86	89	92	95	98	101	104	107	110	113	116	119	122	125
WEIGHT (lbs)		97	103	110	117	123	130	136	143	150	156	163	169	176	183	189	196	202	209	216	222	229	235	242	249	255	262	268	275

Appendix III. Prohibited Drug List

	Drug Category	Major Indications	Type of Impact	Description of Impact	Route	Brand Name	Generic Name	Washout Period*
1 2 3 4 5 6 7 8	Anti-depressant (Tricyclic)	Depression	Safety	May ↑ the cardiovascular side effects	PO	Anafranil Asendin Norpramin Pamelor Sinequan Surmontil Tofranil	Clomipramine Amoxapine Desipramine Nortriptyline Doxepin Trimipramine Imipramine	4 weeks
9 10 11						Elavil	Amitriptyline	
12 13					PO	Desyrel Ludiomil Serzone	Trazodone Maprotiline Nefazodone	
14 15 16 17 18 19 20	Antihistamine	Allergy	Safety	Potentiate side effect of Primatene and Albuterol	PO	Benadryl Chlortrimeton	Diphenhydramine Chlorpheneramine	6 hours
21 22 23 24 25 26 27 28 29	Alpha1-blockers β1/β2-Blockers (Selective & Non-selective)	Hypertension/ Prostate enlargement Hypertension/ angina	PK	↑ PK level by competing for α-receptors	PO	Cardura Dibenzyline Flomax Hytrin Minipress Rapaflo Uroxatral	Doxazosin Phenoxybenzamin Tamsulosin Terazosin Prazosin Silodosin Alfluzosin	3 days 5 days 3 days 3 days 3 days 3 days 3 days 3 days
30						PO/IV	Betapace	Sotolal
31 32 33 34 35 36 37 38 39						PO	Blocadren Bystolic Coreg	Timolol Nebivolol Carvediol
30						PO/IV	Inderal	Propranolol
31						PO	Lopressor	Metoprolol
32						PO	Tenormin	Atenolol
33						PO/IV	Trandate	Labetalol
34						PO	Zebeta	Bisoprolol
35								
36								
37								
38								
39								
30	Cardiac Glycoside	Congestive heart failure	Safety	May induce cardiac arrhythmia with Primatene; Albuterol may ↓ digoxin level	PO	Lanoxin	Digoxin	10 days
31 32 33 34 35 36 37 38 39	Diuretics	Edema/ Hypertension	Safety	ECG changes/ Hypokalemia/ hyperkalemia	PO	Aldactone Bumex Diuril Demadex HydroDiuril Hygrotone Lasix Lozol Zaroxolyn	Spironolactone Bumetanide Chlorothiazide Torsemide Hydrochlorothiazid Chlorthalidone Furosemide Indapamide Metolazone	1 day 3 days 1 day 3 days 1 day

*This drug list is provided based on the drug interaction listed in package insert of Epi-Pen. Some drugs that have been discontinued per FDA website will not be listed here. Asthma medications are also not listed because this study is for healthy volunteers only.

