1.5. Contraindications, Warnings, Precautions, and Adverse Reactions

1.5.1. Contraindications

Epinephrine Inhalation Aerosol is contraindicated in patients who are taking a prescription drug that contains phenylephrine, pseudoephedrine, ephedrine, or caffeine (for allergy, cough-cold, or pain), monoamine oxidase inhibitor (MAOI) (in certain drugs for depression, psychiatric or emotional conditions, or Parkinson's disease), or for 2 weeks after stopping the MAOI drug.

Albuterol Sulfate HFA is contraindicated in patients with a history of hypersensitivity to albuterol and any other Albuterol Sulfate HFA components.

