4.2.4. Exclusion Criteria

Candidates will be excluded from the study for **any** of the following reasons:

- (1) Concurrent clinically significant cardiovascular, hematological, renal, neurologic, hepatic, endocrine, psychiatric, or malignant diseases.
- (2) Known intolerance or hypersensitivity to any component of the study drugs (i.e., Epinephrine, Albuterol Sulfate or any sympathomimetic drugs, HFA-134a, thymol, ethanol, ascorbic acid, nitric acid, and hydrochloric acid).
- (3) Upper or lower respiratory tract infection, or other systemic infection within 6 weeks prior to Screening;
- (4) Clinically significant abnormalities in the screening/baseline ECG; prolonged corrected QT interval (QTcF) on ECG: men >450ms, women: >470ms; single or multiple premature ventricular contractions (PVC);
- (5) Abnormal thyroid function test (if TSH is out of range, refer to T3/T4 for thyroid function assessment);
- (6) Subject has been on other investigational drug/device studies within 30 days of Screening Visit or planned participation in another investigational drug trial at any time during this trial;
- (7) Women who are pregnant or lactating or planning a pregnancy during the study period;
- (8) Subject has donated or lost > 500 mL of blood within 3 months of Screening;
- (9) Evidence of alcohol or drug abuse or dependency within 6 months prior to screening; or
- (10) Use of any of the prohibited drugs listed in [Appendix III](#) without appropriate washout.

4.3. *Randomization Procedures*

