5.2.4. Instruction to Subjects at the End of Screening Visit

- (1) Dates for Dosing Visit-1, Visit-2, and Visit-3 should be separated by 2 to 7 days.
- (2) Subject must be at least 10-hours fasting for each Dosing Visit.
- (3) Subjects must refrain from alcohol consumption and caffeine-containing (including decaffeinated) beverages or foods (coffee, tea, applicable soft drinks including cola and analogs, or chocolate) for 24 hours prior to each Dosing Visit.
- (4) At each Dosing Visit, subjects are required to check in at the site the night before. Dinner will be provided at study site.

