5.3.2. Pre-dose Activities

At each Dosing Visit, the following review and verification will be performed prior to study drug administration:

- (1) A urine or serum pregnancy test must be performed on all female subjects. If it is positive, the subject will be terminated from the study;
- (2) Any concomitant medication since the last visit will be recorded, including name of medication, route of administration, dosage, indication, and start and end dates where available. If any medications listed in [Appendix III](#) were used after the last visit without the proper washout period, the subject will be terminated;
- (3) Perform alcohol and drug test; if any is positive, subject will be terminated;
- (4) Subjects will be trained again on the use of the MDI inhalation aerosols prior to each treatment session, as described in [Section 4.5.1](#);
- (5) Placement of ECG leads;
- (6) Subjects need to rest for at least 10 minutes prior to the baseline vital signs evaluations. Vital signs should be taken from the opposite arm of the IV catheter arm if possible; Vital signs measurement may be repeated twice to PI discretion.
- (7) An indwelling IV catheter shall be placed into one of the antecubital region veins for blood drawing, or separate venipunctures may be used; and
- (8) One (1) baseline blood samples will be collected within 30 minutes before dosing.

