Appendix III. Prohibited Drug List (Continued)

	Drug Category	Major Indications	Type of Impact	Description of Impact	Route	Brand Name	Generic Name	Washout Period*		
40	Monoamine Oxidase-A Inhibitor	Major depression	PK/ Safety	↑PK and cardiac side effects of Primatene and Albuterol	PO	Marplan Nardil Parnate Eldepryl Zelapar Xadago	Isocaarboxazid Phenelzine Tranylcypromine Selegiline Selegiline Safinamide	14 days		
41										
42										
43	Monoamine Oxidase-B Inhibitor	Parkinsonism								
44										
45										
46	Oral Decongestant /Oral or Parenteral Sympathomimetics	Attention Deficit Hyperactivity Disorder (ADHD)	PK/ Safety	↑PK level and ↑cardiac side effects of Primatene and Albuterol	PO	Adderall Adderall XR Dexedrine Ritalin Ritalin LA Vyvanse	Dextroamphetamine mixed salts Dextroamphetamine Methylphenidate Methylphenidate Lisdexamfetamine	2 days 5 days 4 days 2 days 5 days 1 day		
47						Adrenalin	Epinephrine	1 day		
48						Afrin Neo-synephrin	Oxymetazoline Phenylephrine	2 days 1 day		
49		Anaphylaxis			PO	Advil Cold & Sinus	Ibuprofen/ Pseudoephedrine	1 day		
50						Allegra D	Fexofenadine/ Pseudoephedrine			
51						Claritin D	Loratadine/ Pseudoephedrine			
52		Nasal Congestion			PO	Mucinex D	Guaifenesin/ Pseudoephedrine			
53						Sudafed/PE	Phenylephrine			
54						Sudafed/SA	Pseudoephedrine			
55		Allergy/nasal congestion			PO	Zyrtec D	Cetirizine/ Pseudoephedrine			
56										
57										
58		Allergy/Nasal & Chest Congestion			PO					
59										
60										
61										
62	Phenothiazines	Nausea & Vomiting	Safety	May potentiate side effect of Primatene and Albuterol	PO	Compazine	Prochlorperazine	7 days		
63						Etrafon*	Perphenazine/ amitriptyline			
64		Schizophrenia			PO	Mellaril*	Thioridazine			
65						Serentil*	Mesoridazine			
66						Stelazine*	Trifluoperazine			
67					PO/IV	Thorazine*	Chlorpromazine			
	Thyroid hormones	Hypothyroidism	Safety	↑ cardiac effects of Primatene and Albuterol	PO	Synthroid	Levothyroxine	6 weeks		

*This drug list is provided based on the drug interaction listed in package insert of Epi-Pen. Some drugs that have been discontinued per FDA website will not be listed here. Asthma medications are also not listed because this study is for healthy volunteers only.

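### Appendix III names neither ephedrine nor any caffeine-containing medicine, although Section 1.5.1 calls prescription products with these ingredients contraindicated with inhaled epinephrine, so no explicit rule requires exclusion or termination

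*Protocol*

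**What the plan says.** Protocol Section 1.5.1 describes the inhaled epinephrine product, which is Treatment A, as contraindicated for someone taking "a prescription drug that contains phenylephrine, pseudoephedrine, ephedrine, or caffeine (for allergy, cough-cold, or pain"), and for someone taking an MAO inhibitor or within 2 weeks of stopping one.

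Appendix III is the prohibited drug list. Its footnote gives the source: "This drug list is provided based on the drug interaction listed in package insert of Epi-Pen". The category nearest to the Section 1.5.1 ingredients is headed "Oral Decongestant /Oral or Parenteral Sympathomimetics".

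Three rules act on medication, and each refers to that list:

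- Exclusion (10) in Section 4.2.4 begins "Use of any of the prohibited drugs listed in" and then points to Appendix III.
- Section 5.2.3(3), the screening review, checks medication history against Appendix III.
- Section 5.3.2(2), the pre-dose check, says that if Appendix III medicines "were used after the last visit without the proper washout period, the subject will be terminated". The same item also says "Any concomitant medication since the last visit will be recorded", which is not limited to the list.

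Separately, Section 5.2.4(3) tells subjects to avoid "caffeine-containing (including decaffeinated) beverages or foods" for 24 hours before each Dosing Visit. Section 5.3.3(6) repeats the restriction during the visit.

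**The concern.** The protocol states a contraindication in one place and enforces medication rules from a list in another, and the two do not match. The footnote suggests why: the list was drawn from the injection's insert, while the contraindication belongs to the inhaled product. Section 1.6 nevertheless presents Appendix III as the list for both epinephrine and albuterol.

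Healthy volunteers are at stake. Each is due to receive Treatment A at one of three visits. If a subject takes a prescription medicine that the protocol itself calls contraindicated with that treatment, and no written rule tells the site what to do, the outcome depends on individual judgement. That judgement can differ between subjects and between visits.

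**Working it through.** There is no figure to reproduce. The check compares the Section 1.5.1 items with the names in Appendix III and then follows each written rule that could stop a subject.

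**Step 1: could the text extraction have dropped a row?** Brand names in Appendix III by category:

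- antidepressants 11
- antihistamines 2
- alpha-blockers 7
- beta-blockers 9
- cardiac glycoside 1
- diuretics 9
- MAO inhibitors 6
- decongestants and sympathomimetics 16
- phenothiazines 6
- thyroid hormone 1

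The sum is 11 + 2 + 7 + 9 + 1 + 9 + 6 + 16 + 6 + 1 = 68. The rows are numbered 1 to 67, with one unnumbered thyroid row: 67 + 1 = 68. In the category that matters, rows 46 to 61 are 61 − 46 + 1 = 16 rows, against 16 brand names. No row appears to be lost.

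**Step 2: Section 1.5.1 items against Appendix III.**

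| Item in Section 1.5.1 | Named in Appendix III? | Class heading that might cover it |
|---|---|---|
| Phenylephrine | Yes | – |
| Pseudoephedrine | Yes, in several combinations | – |
| MAO inhibitors | Yes; 14 days, matching the 2 weeks in 1.5.1 | – |
| Ephedrine | No | Possibly the sympathomimetics heading |
| Caffeine in a medicine | No | None |

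Three of the five items are named and 5 − 3 = 2 are not.

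**Step 3: the other written checks, for the two unnamed items.**

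- Exclusion (10), Section 5.2.3(3) and the termination clause of Section 5.3.2(2) apply only to what Appendix III lists.
- The caffeine restriction in Sections 5.2.4(3) and 5.3.3(6) is limited to food and drink. Chocolate and decaffeinated coffee are barred; a prescription pain medicine containing caffeine is not mentioned.
- The nine-panel drug screen in Appendix IV has no item for ephedrine or caffeine.
- Exclusion (3), respiratory or other systemic infection within 6 weeks before Screening, would remove some cough-cold users at entry. It does not address allergy or pain medicines. Table 4 schedules the inclusion and exclusion review at Screening and Dosing Visit-1 only, so at Visits 2 and 3 the written medication rule is the Appendix III check.

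**Result.** No explicit rule requires exclusion or termination of a subject taking a prescription allergy, cough-cold or pain medicine that contains caffeine. The same holds for ephedrine unless the class heading is read as a prohibition in itself.

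**The case against.** The strongest case on the other side is that the protocol has further safeguards.

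- All concomitant medication is recorded before each dose, listed or not. The investigator makes the final enrolment decision (Section 5.2.3) and a subject may be discontinued for medical safety (Section 7.1). This stands. A reader might infer that such a subject passes every check and is dosed; the documents do not support that. What they support is that no rule compels either outcome.
- Ephedrine may be read under the sympathomimetics heading, and Section 1.6 names sympathomimetics as a class. This stands in part. The rules refer to drugs that are listed, and washouts in that category run from 1 to 5 days by product, so an unlisted drug has no stated washout to apply. No class covers caffeine, which is why caffeine is the firmer half.
- Section 1.5.1 is limited to prescription products. This stands. The contradiction should not be stretched to non-prescription cold or pain remedies.
- Subjects check in the night before each Dosing Visit (Section 5.2.4(4)), which shortens the unsupervised time before dosing. True, but check-in creates no rule about a medicine already taken.
- Section 1.5.1 is background, and Section 1.6 describes Appendix III as drugs with strong PK or PD impact, not as a contraindication list. That may explain the mismatch. Appendix III is still the list that the exclusion and termination rules use.

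A reader might also infer that such use would distort the crossover comparison. The documents do not support this. Occasional use unrelated to treatment, spread over randomised sequences, adds noise and not a systematic difference. SAP Section 4.1.1 subtracts the same-day baseline from the epinephrine AUC (although not from the maximum concentration), vital signs have a same-visit baseline, and the planned PK analysis is descriptive. Nor do the documents say that caffeine alters endogenous epinephrine.

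**Conclusion.** The point holds as an internal contradiction that bears on safety. Section 1.5.1 and the enforced medication list disagree on two of five items, clearly for caffeine-containing prescription medicines and arguably for ephedrine. Handling of such a subject is left to investigator discretion.

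No number of affected subjects or visits can be given, because the documents contain no rate of use. The conclusion assumes that the rules mean what they say in referring to listed drugs, and that Appendix III is complete as published, which the row count supports. It does not depend on any claim about bias in the PK or safety comparisons. The sponsor should correct it, because the contraindication is the protocol's own and the correction is cheap.

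**What to change.** Reconcile Section 1.5.1, Appendix III, exclusion (10) in Section 4.2.4, and Sections 5.2.3(3), 5.2.4(3), 5.3.2(2) and 5.3.3(6), so that the stated contraindications and the enforced medication list agree. The reconciled text should make clear whether the class headings in Appendix III are prohibitions in themselves or only labels for the named products, and whether the caffeine restriction is meant to extend to medicines. The content and any washout are for the sponsor's medical team to decide.

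The cost is a text edit in a few sections. Depending on what is decided, an occasional visit or subject might be lost.
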